The drug effects will be studied after a single dose of 50 mg albiglutide and a single dose of 10 μ g exenatide using 1) functional magnetic resonance imaging (fMRI) to assess changes in resting-state blood oxygen level dependent (BOLD) signal, 2) arterial spin labeling (ASL), and 3) magnetic resonance spectroscopy (MRS). The highest approved doses will be used to maximize the potential to observe nausea and the timing of the MRI will overlap with C_{max} . Due to the difference in expected time of C_{max} (albiglutide 3-5 days and exenatide 2 hrs), the timing of MRI and other key study assessments relative to dosing are scheduled to coincide with expected C_{max} timing. Placebo is used to maintain the single-blind.

Observing the rotation of vertical stripes in a rotating drum to create the illusion of self motion (vection) is a well characterized stimulus (task) that can serve as a map of the central response to nausea [[name], 2013; Farmer, 2015]. Each subject will be studied under this standardized condition without the study medication to identify the brain circuitry associated with motion sickness induced nausea (an established vection task). Group analyses will then compare brain outcomes (e.g. connectivity) for motion sickness induced nausea versus nausea induced by different drugs to allow the inference of GLP 1R agonist effects in nausea related brain activation. The group activation maps generated from the vection task scans will also be used to define ROIs to better interrogate the drug-induced alterations in other neuroimaging outcomes (i.e. ASL, MRS). Each subject will act as their own control in this crossover design. The resting-state BOLD and cerebral blood flow (rCBF-ASL) will both be used to provide insight into the connectivity of the central nausea response.

By examining BOLD signals at rest and during task, ASL-rCBF changes and assessing in vivo metabolic changes through MRS [glutamate and gamma-aminobutyric acid (GABA) concentrations], the relationship between neurotransmitter concentration and brain activation/deactivation in specific brain regions will be explored.

The information from this study is expected to be of benefit for patients in the future, as insights on the mechanisms of nausea associated with GLP 1 receptor agonists are needed to design new strategies to minimize the occurrence and impact of these AEs with drugs currently in use, and to design new drugs able to avoid these mechanisms.

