In both Part A and Part B, subjects who meet the eligibility criteria will be randomized in a crossover fashion to one of 4 different sequences, each consisting of two dosing/imaging sessions (Session 1 and Session 2) separated by a 6-9-week washout period (Section 4.2 Table 1). Each subject will undergo a single off-therapy MRI during a separate Visit according to the randomization sequence to minimize the total number of scans per subject. The timing or sequencing of the off-therapy MRI will be randomized (i.e. Session 1 or Session 2) to account for potential learning effects. Each subject will undergo one off-therapy MRI, one post-dose albiglutide MRI and one post-dose exenatide MRI for a total of 3 MRI scans during the study. The visit schedule is set to allow the Off-therapy MRI scan visit to occur approximately 7 days prior to the post-dose scan within the Session as this is the minimal recommended time between scans. The visit on Day 5 allows the dosing of albiglutide or albiglutide placebo to occur 4 ± 1 days before the post-dose MRI i.e., at estimated T_{max} (3-5 days). Because of the short T_{max} (2 hrs) for exenatide, exenatide or saline placebo is given on the day of the MRI scan (Day 8). Therefore, MRI Session 1 and Session 2 each consist of 2 or 3 single-day out-patient visits according to the randomization schedule on the following days:

- Day 1 (Either Session 1 or 2 per randomization) for an off-therapy MRI scan consisting of resting-state fMRI, a nauseogenic task fMRI, ASL and MRS and nausea associated assessments,
- Day 5 for a single dose of 50 mg albiglutide or albiglutide placebo, and
- Day 8 for a single dose of 10 μ g exenatide or saline placebo followed by a post-dose MRI scan consisting of resting-state fMRI, ASL and MRS, and nausea associated assessments.

Subjects will be blindfolded when receiving the study medication injection to maintain the single-blind.

For all MRI sessions, subjects must fast overnight and will be instructed to refrain from eating and drinking anything but water starting at approximately 10 pm the night before or with in 8 hours of the start of their MRI appointment.

For the off-therapy session, MRI scan and nausea associated assessments will be conducted without prior injection (no drug, no placebo).

On post-dose scanning visits, subjects will be offered a meal after the procedure before leaving the unit, and capillary glycemia will be assessed.

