This exploratory study will include exenatide, a well-studied short-acting GLP-1 receptor agonist, as the active control. Exenatide has been shown to induce nausea at an incidence of 61.7% after a single 10 µg dose in healthy volunteers over 24 hrs post-dose [Ellero, 2010]. Temporal changes in the fMRI BOLD signal were observed after a single 5 µg dose of exenatide [McKie, 2013]. The timing of the MRI is chosen to coincide with albiglutide and active control expected Tmax. Therefore, the MRI is planned in 3 days for albiglutide but conducted after 1 hr for exenatide. The washout period between injections is 6-9 weeks due to the long half-life of albiglutide (T1/2= 5 days). Six to nine weeks will allow the scheduling of the scan visits to be aligned with the same phase of the menstrual cycle, when possible, for women of reproductive age.

This exploratory study includes placebo (albiglutide placebo or saline subcutaneous injection) to maintain the subject's blind and account for potential central activation that may result from receiving an injection prior to the MRI scan.

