- h. All MRI include resting-state fMRI, ASL and MRS. Off-therapy MRI scan includes visual nauseogenic task fMRI and can be initiated once -assessments are completed. The on-therapy scan should be initiated 1 hr ±15min post the exenatide or exenatide placebo dose. Pre-scan procedure timings are suggested times to allow completion of activities. Post MRI procedure should be completed at the noted times ±15 min.

- i. MSAQ is given following the VAS.
- j. Subjects will be offered a snack prior to leaving the site.
- k. Only events related to the Study Procedures meeting the SAE criteria are reported after screening and before dose on Session 1 Day 5.
- l. Subjects should remain at the site for at least 1 hr after completion of MRI. All procedures and assessments must be complete prior to discharge. The Investigator will approve the release of the subject from the clinic, or will provide treatment for the standard of care as required.
- m. The Post-dose MRI **MUST** be scheduled 4 ± 1 days after the albiglutide or albiglutide placebo dose. The day of dosing albiglutide is counted as the first day.

Procedure	Screening		Session 1						Wash out	Session 2						F/U							
	Week -4 to -1		Day 1	Day 4±1 ^m					6-9 weeks	Day 1			Day 5±1 ^m	Day 8±1 ^m					Week 13				
	1	2		-2h	-0.5h	0h	0.5h	1h		Post MRI	Pre-MRI	MRI		Post MRI	0.5h	1h	-2h	-0.5h		0h	0.5h	1h	Post MRI
Visit (all out-patient)	1	2	3	4							5			6	7					8			
Dosing albiglutide or placebo ^g			X									X											
Dosing exenatide or placebo ^g					X											X							
MRI ^h								X			X								X				
Autonomic monitoring								X			X								X				
Electrogastrogram								X			X								X				
VAS						X		X			X	X				X			X				
MSAQ ⁱ								X			X								X				
Capillary blood glucose								X											X				
Fasting Plasma Glucose								X											X				
Snack ^j								X			X								X				
AE assessment ^k			X	←-----→							←-----→			X	←-----→					X			
Discharge ^l								X				X							X				X

- a. Medical history includes alcohol/tobacco/caffeine usage.
- b. Prior-Medications are defined as prescription or over-the counter medications taken within 30 days of Screening. Record concomitant medications and or changes
- c. WCBP is women of child-bearing potential. Serum pregnancy test at Screening. Urine pregnancy at other specified time points
- d. If test otherwise performed within 1 month prior to first dose of study treatment, testing at screening is not required

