7.3. Endpoints

7.3.1. Magnetic Resonance Imaging

All MRI assessments will be acquired on a Siemens 3T system located at the Martinos Center for Biomedical Imaging. All Martinos scanners undergo quality assurance (QA) assessments every morning to ensure that fMRI signal drifts and variances are within limits and that signal spiking is not occurring.

Imaging scans will be reviewed by trained technologists and abnormal findings will be consulted with a radiologist. Subjects will be advised to seek consultation based on the radiologist's opinion.

Structural MRI:

Structural MRI data will be collected prior to all fMRI and MRS data collection using a T1-weighted magnetization-prepared rapid gradient-echo (MP-RAGE) pulse sequence. These data will be used to help align functional data to the MNI space, while exploratory analysis of gray matter volume and cortical thickness can be related to functional brain response and symptom severity.

Functional MRI

All fMRI analyses will use a combination of tools, previously validated, and used in the [name] Lab for the analysis of similar data. Tool packages will include: FSL (FMRIB Software Library; <http://www.fsl.fmrib.ox.ac.uk/fsl/>), AFNI (Analysis of Functional NeuroImages; <http://afni.nimh.nih.gov/afni>), and FreeSurfer (<http://surfer.nmr.mgh.harvard.edu/>).

BOLD fMRI Resting

Resting functional connectivity will be assessed using data acquired in the first 6 minutes of the vection task scan run, i.e. when the subject is resting, before any motion sickness provocation during the Off-therapy scan. For on-drug MRI visits, a separate 6-minute BOLD fMRI resting state scan will be performed, and subjects will verbally rate (0-100 NRS) their nausea intensity before and after this scan. Data will be analysed using validated independent component analysis (ICA) methods and seed voxel connectivity methods using functional localizer seeds obtained from the results of the motion sickness fMRI analyses.

BOLD fMRI Visual Nauseogenic Task

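### The albiglutide scan window, as counted, is 2-4 elapsed days rather than the 3-5 day Tmax it is said to match; secondarily, the exenatide start rule does not by itself secure timing at 2 h

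*Protocol*

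**What the plan says.** Protocol Section 4.4 states the intention: "The timing of the MRI is chosen to coincide with albiglutide and active control expected Tmax". It then gives the nominal intervals: "Therefore, the MRI is planned in 3 days for albiglutide but conducted after 1 hr for exenatide". The data-point table in Section 9.3 labels both on-drug scans as being at Tmax. Section 2.1 makes a weaker claim, that "the timing of the MRI will overlap with C_{max".

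**Albiglutide.** Section 4.1 describes the Day 5 dose as falling 4 ± 1 days "before the post-dose MRI i.e., at estimated T_{max} (3-5 days"). Footnote m to both Time and Events tables makes 4 ± 1 days mandatory and adds: "The day of dosing albiglutide is counted as the first day".

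**Exenatide.** Section 4.1 explains same-day dosing by the drug's kinetics ("Because of the short T_{max} (2 hrs) for exenatide"), and Section 2.1 also gives Tmax as about 2 h. Footnote h, repeated in SAP Section 10.2.1, sets the start: "The on-therapy scan should be initiated 1 hr ±15min post the exenatide or exenatide placebo dose". For the order of acquisition, Section 7.3.1 says: "Structural MRI data will be collected prior to all fMRI and MRS data collection". It gives the post-dose resting BOLD run a length of 6 minutes. Neither document gives the total session length or the post-dose order of resting BOLD, ASL and MRS.

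**The concern.** The on-drug scans are meant to capture each drug at peak exposure, and the protocol describes them that way. For albiglutide, the text in Section 4.1 and the counting rule in footnote m cannot both be right. A 4 ± 1 day interval equals 3-5 days only if the dosing day is day 0. For exenatide, the rule fixes only when the scan starts, and that is 45-75 min before the stated Tmax.

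What is at stake is the exposure at which resting BOLD, rCBF, glutamate and GABA are measured, and whether that exposure is similar across subjects and modalities. It bears on the albiglutide-exenatide contrast in Section 9.3. It also bears on the off-therapy versus exenatide comparisons, which are what SAP Section 11.1.1 describes for resting-state fMRI and pCASL.

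**Working it through.** **1. Reproduce the nominal intervals.** Day 8 − Day 5 = 3 elapsed days. In a session without the off-therapy scan, Day 4 − Day 1 = 3. Both agree with the 3 days in Section 4.4, and 3 lies within 3-5.

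**2. Albiglutide window.** With dosing as day 1, elapsed days = counted day − 1. Counted days 3, 4 and 5 give 2, 3 and 4 elapsed days. The second schedule confirms this reading: dose on Day 1, scan on Day 4 ± 1, so the scan falls on Days 3-5, again 2-4 days later. The visit windows alone (Day 5 ± 1 and Day 8 ± 1) would allow (8 − 1) − (5 + 1) = 1 to (8 + 1) − (5 − 1) = 5 elapsed days. Footnote m narrows that to 2-4. With dosing as day 0, the same 4 ± 1 would be 3-5, as Section 4.1 says.

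**3. Exposure at each elapsed day.** I assume a one-compartment model with first-order absorption: C(t) = ka/(ka − ke) × (exp(−ke·t) − exp(−ka·t)), ke = ln 2 / half-life, and ka solved from Tmax = ln(ka/ke)/(ka − ke). The half-life of 5 days is from Section 4.4. Per cent of Cmax:

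| Elapsed days | Tmax 3 d | Tmax 4 d | Tmax 5 d |
|---|---|---|---|
| 2 | 94.0 | 83.4 | 73.4 |
| 3 | 100 | 96.6 | 89.8 |
| 4 | 96.5 | 100 | 97.8 |
| 5 | 88.9 | 97.6 | 100 |

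The lowest value is 73% in the 2-4 day window and 89% in a 3-5 day window.

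**4. Exenatide intervals.** The start is at 60 ± 15 min, that is 45, 60 or 75 min. To reach 120 min, the session must last at least 120 − start = 75, 60 or 45 min. To be centred on 120 min, it must last twice that: 150, 120 or 90 min. A 6-min resting BOLD run beginning 5-30 min into the session (assumed offset) ends no later than 75 + 30 + 6 = 111 min, before 2 h.

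**5. Exenatide exposure.** Same model, Tmax 2 h. The half-life is not in the documents; I assume 1-4.8 h. At the start itself, exposure is 70-75%, 82-86% and 91-93% of Cmax for 45, 60 and 75 min. Session means, per cent of Cmax:

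| Session length | Start 60 min | Start centring on 2 h | Gain |
|---|---|---|---|
| 60 min | 95-96 | 99 (start 90 min) | about 3-4 points |
| 90 min | 96-97 | 98 (start 75 min) | about 1-1.5 points |
| 120 min | 96-97 | 96-97 (start 60 min) | none |

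At the edges of the start window, a 60-min session averages 89-91% from 45 min and 98% from 75 min. If Tmax is really 1.5 or 2.5 h, a 60-min session from 1 h averages 98-99% or 88-90%.

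**The case against.** The strongest reply is that little exposure is lost.

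- **Albiglutide.** The planned interval is inside the Tmax range. The 73% figure needs both the earliest permitted day and a Tmax at the 5-day limit; with Tmax at 3 days the same scan is at 94%. This stands as to size. The rule still permits a scan before the stated range and rules out a day within it.
- **Exenatide.** Tmax is approximate, Section 2.1 promises only overlap with Cmax, and structural imaging takes up the first part of the session, so no endpoint is measured at the start-time percentages. A session with structural MRI, BOLD, whole-brain ASL and 3D spectroscopy may well run past 2 h. All of this stands, and for a 2 h session the present start is already right. What remains is that overlap by the session does not place each endpoint at Tmax.
- **Pilot status.** Part A was meant to test acquisition parameters, so some open detail is reasonable. That excuses the missing order and length, but not the contradictory day count.
- **Relevance now.** SAP Section 1 records that Part B was cancelled, and SAP Section 11.1.1 describes its exenatide scans as post-dose, not as at peak. This stands, and it limits the remedy mainly to reporting and reuse.

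A reader might infer that the scans missed peak exposure, or that the drug comparison is biased. The documents do not support either. They give the nominal albiglutide interval as 3 days, no actual scan times, and no concentration-response relation or effect delay.

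**Conclusion.** The albiglutide window is wrong as written, with modest effect: the binding rule gives 2-4 elapsed days where Section 4.1 claims 3-5. This needs only the protocol's own figures.

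The exenatide point is weaker. The at-Tmax label in Section 9.3 holds only if the session lasts at least 45-75 min, depending on the start, and each endpoint is acquired late enough. The start rule does not ensure this, but it does not show a mistimed scan either. The probable shortfall from the nominal start is about 3-5% of Cmax averaged over the session. That figure rests on a one-compartment model, an assumed half-life, a Tmax of exactly 2 h and session lengths of 1-2 h. The effect on the imaging endpoints cannot be sized from the documents.

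**What to change.** **If the schedule is used again:**

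1. Define the albiglutide window as 3-5 elapsed days, in the same terms in Section 4.1 and footnote m. If slack of ±1 day is needed, move the nominal dose one day earlier relative to the scan: Day 4 to Day 8, or Day 1 to Day 5 in a session without the off-therapy scan. The cost is slightly tighter or shifted scheduling. The 7 days between the off-therapy and post-dose scans are unaffected.
2. State the post-dose session length and modality order, use the same order at both post-dose scans, and set the start so that the endpoint acquisitions bracket 2 h after exenatide or saline. A workable rule is start = 120 min minus half the session length: 90 min for a 1 h session, 75 min for 1.5 h, and no change for 2 h. The cost is 30, 15 or 0 min more waiting and fasting after a drug that may cause nausea. The pre-scan VAS moves with the start, to stay about 30 min before it (Section 7.3.4).

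Centring does not put every modality at the same exposure; the fixed order makes the differences consistent between the two post-dose scans.

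**For the completed Part A:** list minutes from the exenatide or saline dose to each acquisition, and elapsed days from the albiglutide dose. Do not describe exenatide data acquired before about 2 h as being at Tmax. Dose times are already recorded (Section 6.7), and acquisition times would come from the imaging laboratory, so the cost is small.

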9.3. Data Analysis Considerations

There will be 4 fMRI and 3 MRS data points as shown in the table below:

Treatment Period ^a			Albiglutide	Exenatide
Day Relative to Period Start ^b	1 Off-therapy	1 Off-therapy	8 At T-max	8 At T-max
Visual Nauseogenic Task	No	Yes	No	No
MRI Data Point (DP)	DP1	DP2	DP3	DP4

Treatment Period ^a			Albiglutide	Exenatide
Resting State BOLD fMRI	✓		✓	✓
Nauseogenic task based BOLD fMRI		✓		
ASL	✓		✓	✓
MRS	✓		✓	✓

^a The order of the treatment periods will be randomized.

^b The day is relative to start of the Treatment Period.

For each subject, the Off-therapy Day 1 assessment(s) (DP1 and/or DP2 in table above) during the dosing/imaging sessions will serve as the baseline fMRI assessment.

Nauseogenic task BOLD signal (DP2,) will be assessed only during the off-therapy fMRI session. For the BOLD endpoint, the main contrasts of interest are the differences in the connectivity between albiglutide and off-therapy (DP3-DP2), between Exenatide and off-therapy (DP4-DP2), and between Albiglutide and Exenatide (DP3-DP4).

For resting state analysis rCBF ASL endpoints, the contrasts of interest are the differences DP3-DP1, DP4-DP1, and DP4-DP3. Similarly, for GABA and Glutamate concentrations, the main contrasts of interest are the differences DP3-DP1, DP4-DP1, and DP4-DP3.

The vection-induced nausea will provide a reference to regions of nausea associated brain activity. A group map will be calculated as in the previous Martinos Center study, and regions of interest (ROI) will be defined from the group map. These ROIs will then be used to perform masked comparison analyses for rCBF and MRS (where possible) data between the albiglutide vs exenatide and drug vs no-drug conditions. Such targeted analyses will allow for greater power than whole brain analyses which will need to be more stringently corrected for multiple comparisons.

There will be no imputation for missing data. Subjects who only partially complete the study may be included in some of the analyses where appropriate, depending on which data are available and which are missing.

Summary statistics (including number of subjects, mean, median, min, max, SD, SE) will be reported for continuous variables. The frequency and percentage will be used to summarize categorical variables.

Functional MRI Data

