11. ATTACHMENTS [DOCUMENTATION FROM MARTINOS]

11.1. Reporting & Analysis Plan for Imaging Data for Part A

11.1.1. Overview of Quality Control for Imaging Data

Quality control procedures will include visual inspection of raw brain images for presence of various artifacts, including but not limited to, aliasing, excessive distortion, Nyquist N/2 ghosting, and signal inhomogeneities. We will also assess head motion correction parameters to ensure that subjects were not moving excessively during the functional MRI (BOLD fMRI and pCASL) scans. We will evaluate 1) total translation and rotation motion, 2) relative TR-to-TR motion, 3) number of relative translations (> 0.1 mm). For pCASL data, we will calculate rCBF and ensure values within the gray matter are within normal bounds (40-60 mm/100 g tissue/min). For ¹H-MRS data we will assess spectra to ensure adequate SNR (Cramer–Rao lower bounds values below 40%).

We will perform single-subject level analyses and include data from (1) resting-state BOLD fMRI, (2) pseudo-continuous arterial spin labelling (pCASL), and (3) proton-density weighted magnetic resonance spectroscopy (¹H-MRS).

Primary Outcomes/Endpoints:

1. Resting-state functional connectivity (resting-state BOLD fMRI)
2. Regional cerebral blood flow (rCBF) (pCASL)
3. Glutamine/Glutamate (Glx) and GABA concentrations (¹H-MRS)

1. Resting-state fMRI (rs-fMRI)

Resting-state BOLD signal MRI data collected at off-therapy and exenatide post-dose MRI scan sessions will be analyzed using a whole-brain seed-to-voxel approach. The seed-to-voxel driven approach will include *a priori* seed ROIs placed in brain areas subserving nausea-related processing including regions identified from our prior study ([name] et al. Cereb Ctx 2013). These regions will include: interoceptive/sensory (insula, dACC), emotional/affective (amygdala, pgACC), and cognitive/evaluative (dlPFC/OFC) brain areas, primary visual (V1) and extrastriate cortices (area MT+/V5). Group analyses will be performed using a paired t-test (off-therapy vs. exenatide) with FSL's FLAME (FMRIB's Local Analysis of Mixed Effects).

2. pCASL

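### Placebo matches the injection only between albiglutide and exenatide, so every drug-versus-off-therapy imaging contrast combines the drug with the injection procedure and the scan context

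*Protocol*

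**What the plan says.** **Purpose of placebo.** Protocol Section 4.4 gives placebo two jobs: to keep the subject blind and to "account for potential central activation that may result from receiving an injection prior to the MRI scan".

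**What precedes each scan.** Under Protocol Section 4.1 both sessions include "Day 5 for a single dose of 50 mg albiglutide or albiglutide placebo", and then "exenatide or saline placebo is given on the day of the MRI scan (Day 8". The Time and Events footnotes start the on-therapy scan 1 hour ± 15 minutes after that second injection. The off-therapy scan is "conducted without prior injection (no drug, no placebo". The full set of scans is fixed: "Each subject will undergo one off-therapy MRI, one post-dose albiglutide MRI and one post-dose exenatide MRI for a total of 3 MRI scans".

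**How the scans are compared.** In Protocol Section 9.3 the off-therapy assessment "will serve as the baseline fMRI assessment". The contrasts listed there are:

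- ASL, glutamate and GABA: DP3-DP1, DP4-DP1 and DP4-DP3
- BOLD: DP3-DP2, DP4-DP2 and DP3-DP4, where DP2 is the vection-task scan

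Section 9.4 says these contrasts will be tested. Section 9.3 reads the results as drug effects: it speaks of sub-threshold brain changes caused by the drug, and of the blood-flow response to nausea that the drug induces.

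**SAP.** Attachment 11 (Section 11.1.1) states for resting-state fMRI: "Group analyses will be performed using a paired t-test (off-therapy vs. exenatide". It also compares off-therapy with exenatide for pCASL, at subject level. SAP Section 2.1 says that group analysis of the four Part A subjects will not be completed.

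**The concern.** The protocol itself names activation from being injected as something that could distort the scans. Its remedy, placebo, reaches only one of the comparisons it plans. A reader of Section 4.4 could take the drug-minus-off contrasts to be protected as well, and Section 9.3 encourages this by describing them in terms of the drug.

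At stake is attribution. A difference in connectivity, blood flow or neurotransmitter level between a post-dose scan and the off-therapy scan could be reported as an effect of a GLP-1R agonist when some or all of it comes from the injection procedure or from the different setting of the two scans. The SAP makes this more pressing. The imaging comparisons it names are off-therapy versus exenatide, while the comparison that placebo does protect, albiglutide versus exenatide, has no specified imaging test.

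**Working it through.** The plan states no alpha, effect size or SD for these contrasts, so there is no figure to reproduce. The question is what each contrast can estimate.

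**Model.** Write each data point as a mean plus four terms: A (albiglutide), E (exenatide), J (injection procedure plus any other difference in context between a post-dose and an off-therapy scan) and V (vection task). The entries come from Protocol Sections 4.1, 4.2 and 9.3.

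| Data point | A | E | J | V |
|---|---|---|---|---|
| DP1 off-therapy, rest | 0 | 0 | 0 | 0 |
| DP2 off-therapy, task | 0 | 0 | 0 | 1 |
| DP3 post-albiglutide | 1 | 0 | 1 | 0 |
| DP4 post-exenatide | 0 | 1 | 1 | 0 |

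**Contrasts, by subtracting rows.**

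- DP3-DP1 = A + J
- DP4-DP1 = E + J
- DP3-DP2 = A + J - V
- DP4-DP2 = E + J - V
- DP4-DP3 = E - A, so J cancels

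The SAP's resting-state and pCASL comparisons have the form DP4-DP1, apart from sign.

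**Estimability.** With the mean there are 5 parameters, and the design matrix has rank 4. Add any amount k to J and subtract k from both A and E: all four cell means are unchanged. The data therefore cannot separate A or E from J. Only E - A is free of J. The crossover does not help, because J is present at every post-dose scan and absent at every off-therapy scan in every subject. Randomizing the session of the off-therapy scan deals with learning effects, not with J. A placebo-only scan would raise the rank to 5 and make A and E estimable, but none was planned.

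**Extent.** Four primary imaging endpoints (resting BOLD, rCBF, glutamate, GABA) with three contrasts each give 4 × 3 = 12. Of these, 4 × 2 = 8 are drug minus off-therapy.

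**Illustration with assumed inputs.** Suppose the drug effect is zero and J equals δ standard deviations of the paired difference. For one uncorrected two-sided 5% paired t-test, the rejection probability is 1 - F(t) + F(-t). Here F is the noncentral t distribution with n - 1 degrees of freedom and noncentrality δ√n, and t is the central 97.5% point. For n = 4 and δ = 0.5 the noncentrality is 0.5 × 2 = 1.0.

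| Assumed δ | n = 4 | n = 24 | n = 28 |
|---|---|---|---|
| 0.2 | 6.0% | 15.6% | 17.5% |
| 0.5 | 11.1% | 65.0% | 72.3% |
| 1.0 | 28.9% | 99.7% | 99.9% |

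Part A completed 4 subjects; 24 and 28 were the planned totals. The values of δ are a range, not estimates. The table shows only that more subjects make a shift in J easier to detect and do not remove it.

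**The case against.** **The Section 4.4 sentence is true for the comparison it serves.** The primary objective is albiglutide versus exenatide, and Section 4.1 presents placebo as the means of dosing the two drugs at different times before the scan without breaking the blind. For that comparison, injection number and timing match. This stands: the sentence lacks a limit on its scope, and it would be wrong to infer that placebo fails altogether.

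**The direction of expectation is unknown.** It is tempting to say that expecting nausea pushes every subject's drug-minus-off difference the same way, so that the bias equals the full injection-plus-expectation effect. The documents do not support that. Off-therapy resting BOLD is the first 6 minutes of the vection run, and off-therapy ASL and MRS also precede the task (Section 7.3.1). Subjects were selected for motion-sickness susceptibility (Section 5.1) and rehearsed the stimulus in the mock scanner (Section 7.2.3). They may expect nausea at least as much before the off-therapy task as after a blinded injection. Injection exposure is one-sided; expectation may not be.

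**The SAP group test may not be run.** Section 2.1 rules out group analysis and Attachment 11 opens with subject-level analysis before naming the t-test. This stands, and the point cannot rest on that test alone. A subject-level exenatide-minus-off difference contains the same J.

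**Matching between the drugs is not perfect.** Saline replaces a matched exenatide placebo. Volume agrees (10 µg at 250 µg/mL is 0.04 mL, the saline volume in Section 6.1), needle size is the same and subjects are blindfolded (Section 6.4), but complete cancellation of J is an assumption.

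**The study is exploratory, and a single off-therapy scan was chosen to limit scanning.** Both are fair. They relax error control and explain the design; they do not change what a contrast estimates.

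**Conclusion.** The point holds with limited scope. Placebo accounts for the injection in albiglutide versus exenatide and in no other planned contrast. All 8 drug-minus-off contrasts in the protocol, and the SAP's off-therapy versus exenatide comparisons, combine the drug with the injection procedure and any difference in expectation. Those using DP2 also subtract the vection effect. The size of the combined term cannot be obtained from the documents, and the sign of its expectation part is not known.

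A reader might infer that drug effects should instead be claimed on DP4-DP3. That goes too far. DP4-DP3 estimates E - A, so two equal drug effects would give zero, and it cannot show that either drug acts on its own.

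The conclusion assumes that J is the same after both drugs, which matched injection number and timing make reasonable but do not prove. It does not depend on the assumed δ values. The point should be addressed because it changes what may be said about the results, not how they are collected.

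**What to change.** 1. **Protocol Section 4.4:** state that placebo accounts for injection-related activation in the albiglutide-exenatide comparison only.
2. **Protocol Section 9.3 and SAP Attachment 11:** label DP3-DP1, DP4-DP1, DP3-DP2, DP4-DP2 and the SAP's off-therapy versus exenatide comparisons as combined drug-plus-injection/context effects, not attributable to the GLP-1R agonist alone. For the DP2 contrasts, add that the vection task is also part of the difference.
3. **Same places:** identify DP4-DP3 as the only injection-matched contrast, and say that it estimates the difference between the drugs and neither drug's own effect. This does not require a new test in four subjects; if one is added to the SAP, it is an additional analysis and should be described as such.
4. **SAP Sections 2.1 and 11.1.1:** reconcile the decision against group analysis with the planned paired t-test. If only subject-level comparisons are reported, the label in item 2 applies to them.

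No new scans or subjects are needed, and the changes can still be made in the Part A reporting. The cost is a narrower claim: drug-versus-off results can be described, but not attributed to the drug alone.
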